3.1 Primary endpoint

The primary endpoint of the present study is the identification of difference in the symptoms remission rate, within one month postoperatively, between the ligation and hemorrhoidopexy technique and the conventional ligation of hemorrhoidal arteries using ultrasound, in patients with non-complicated hemorrhoids. If the symptoms are treated then it will be defined as=1 'YES' If the symptoms are not treated then it will be defined as=0 'NO'. The time frame will be 1 month postoperatively.

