5.1 Sample Size calculation

The calculation of the sample size is based on the primary endpoint. According to the literature, the rate of the remission rate of symptoms, of patients who were submitted to hemorrhoidal artery ligation using ultrasound is 72.5%, while the respective rate of the ligation and hemorrhoidopexy technique is 90%. Therefore for a non-inferiority trial, with $\alpha= 2,5\%$, $\beta= 80\%$ and a non inferiority limit of 10% , the calculated sample for each group is 30 patients. Totally, the required number of patients is 60.

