5.3 Statistical Procedures

The statistical estimations of this study will be based on a per protocol analysis. Prior to any computation, all data will be submitted to a Shapiro-Wilk normality test.

Continuous variables will be compared on the basis of an independent samples t-test, whereas for categorical variables, the Pearson chi-square test will be applied.

The effect of the various patient characteristics on the primary and secondary endpoint will be evaluated by a regression analysis. More specifically, a multiple linear and a logistic regression will be used for continuous and categorical variables, respectively.

Regression analysis will be applied to all distinct endpoints. The validity of the linear regression model will be confirmed by the assessment of the following assumptions:

- Independence of observations, assessed by the Durbin-Watson test
- Linear relationship between the dependent variable and each of the independent variables and between the dependent variable and all the independent variables, collectively.
- Homoscedasticity of the data
- Multicollinearity of the data
- Absence of significant outliers, high leverage points or highly influential points
- Normal distribution of the residuals

A Forward model will be introduced in our multiple linear regression analysis. The proportion of variance explained by our model will be represented by R square. The statistical significance of our model will be evaluated by the F-test. The effect of each independent variable on the dependent outcome will be provided by the respective coefficient and the 95%CI.

Similarly, a Forward model will be applied in our logistic regression analysis. The following assumption will be tested:

- Independence of observations and mutual exclusive and exhaustive categories
- Linear relationship between any continuous independent variable and the logit transformation of the dependent variable

The explained variance will be presented by the Cox & Snell R square and Nagelkerke R square test. The percentage of the correctly classified observations will be also estimated. The statistical significance of each variable will be calculated by the Wald test. The odds ratios of each variable will be also estimated, alongside the respective 95%CI.

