The variations between the different time endpoints SF-36 measurements will be evaluated on the basis of a repeated measures ANOVA model. Violation of the sphericity assumption will be determined by the Mauchly's test of Sphericity. In case of significant results, a Greenhouse-Geisser correction will be applied. Post-hoc comparisons will be performed with the introduction of Bonferroni corrections. The effect of the allocation group on the measured group will be quantified by the use of the F-test.

Continuous data will be reported as Mean (Standard Deviation), while categorical data will be reported as N (Percentage). Statistical significance will be considered at the level of p value < 0.05. All analyses will be performed in the IBM SPSS Statistics v23 software

4.LITERATURE

2. Chan A-W, Tetzlaff JM, Altman DG, et al. SPIRIT 2013 statement: defining standard protocol items for clinical trials. *Ann Intern Med* 2013;158:200–7.
3. Henderson AR. Testing experimental data for univariate normality. *Clin Chim Acta* 2006;366:112–129.

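### The trial is sized for non-inferiority with a 10-point margin, but the SAP compares the primary endpoint only with a chi-square test for a difference, so non-inferiority is never tested

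*SAP*

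**What the plan says.** **Design.** SAP 5.1, which repeats protocol 3.8, derives the sample size under a non-inferiority design ("Therefore for a non-inferiority trial") with alpha 2.5% and "a non inferiority limit of 10" percent. The planning rates are given as "hemorrhoidal artery ligation using ultrasound is 72.5" percent for the Doppler-guided control and "the respective rate of the ligation and hemorrhoidopexy technique is 90" percent for the new technique. The result is that "the calculated sample for each group is 30 patients".

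**Endpoint.** SAP 3.1 and protocol 3.6 define remission at one month as yes/no. They state that the endpoint "is the identification of difference in the symptoms remission rate".

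**Analysis.** SAP 5.3 gives one between-arm method for such a variable: "for categorical variables, the Pearson chi-square test will be applied". It closes with "Statistical significance will be considered at the level of p value < 0.05".

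SAP 5.3 also plans forward logistic regression on every categorical endpoint, to assess the effect of patient characteristics. It reports Wald tests and odds ratios with 95% confidence intervals. The covariate list in SAP 4.6 does not include allocation group.

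The 10% limit appears only in the two sample-size sections.

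**The concern.** The sample size and the analysis address different hypotheses. The sample size asks whether the new technique could be worse than Doppler-guided ligation by 10 points or more. The chi-square test asks whether the two rates are equal. The second does not settle the first:

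- A non-significant chi-square result says nothing about whether a 10-point loss has been excluded. With 30 per arm it is the likely result even when the loss is real.
- A result that excludes a 10-point loss can still have p above 0.05, and would then be reported as not significant.

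The planned regression does not fill the gap. No margin is set on the odds-ratio scale, no step converts the odds ratio to a difference in rates, and allocation group may not be in the model.

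At stake is the trial's main conclusion. Without a rule fixed in advance, the choice between a p-value and a margin, and the choice of interval method, would be made after the data are seen.

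**Working it through.** **Inputs (SAP 5.1, protocol 3.8).** Control rate pC = 0.725; new-technique rate pT = 0.90; margin m = 0.10; alpha 2.5%; n = 30 per group; 1:1 allocation (protocol 3.9). Three readings are assumed because together they reproduce the stated n: alpha is one-sided, the margin is absolute, and the figure written as β = 80% is power.

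**1. Reproduce the stated sample size.** Non-inferiority formula, unpooled variance:

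n = (z₀.₉₇₅ + z₀.₈₀)² × [pC(1−pC) + pT(1−pT)] / (pT − pC + m)²

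- Variance term: 0.725×0.275 + 0.90×0.10 = 0.289375
- (1.960 + 0.842)² = 7.849
- Denominator: (0.175 + 0.10)² = 0.075625
- n = 7.849 × 0.289375 / 0.075625 = **30.03**

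This agrees with 30, apart from rounding. One-sided 5% would give 24, and 90% power would give 41.

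**2. Sample size for the planned test.** Two-sided 5% test of a difference, mean rate p̄ = 0.8125:

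n = [1.960×√(2p̄(1−p̄)) + 0.842×√0.289375]² / 0.175² = 76.9, so **77 per group** (88 with continuity correction).

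**3. Power at 30 per group, normal approximation.**

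- Standard error, unpooled: √(0.289375/30) = 0.0982. Pooled: √(2×0.8125×0.1875/30) = 0.1008.
- Margin rule: Φ(0.275/0.0982 − 1.960) = **80.0%**
- Chi-square: Φ((0.175 − 1.960×0.1008)/0.0982) = **40.9%**

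**4. Exact check.** Enumeration of all binomial outcomes with 30 per arm. The margin rule is that the lower limit of the two-sided 95% interval for new minus control is above −10 points.

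| True rates, control / new | Chi-square p < 0.05 | Chi-square p ≥ 0.05 | Margin rule met, Wald | Margin rule met, Newcombe |
|---|---|---|---|---|
| 72.5% / 90% (planning) | 41.6% | 58.4% | 81.0% | 77.5% |
| 72.5% / 62.5% (worse by the margin) | 12.6% | 87.4% | 2.7% | 2.7% |
| 90% / 80% (worse by the margin) | 19.4% | 80.6% | 3.2% | 2.0% |

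Every outcome that is significant in favour of the new technique also meets the margin by Newcombe. At the planning rates, 77.5% − 41.6% = about **36%** of trials therefore meet the margin with p ≥ 0.05.

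**5. Two possible results (Newcombe intervals).**

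- New 27/30, control 22/30: difference +16.7 points, p = 0.095, 95% CI −3.3 to +35.6. Not significant under the SAP, yet non-inferior by the margin. The Wald interval, −2.5 to +35.8, gives the same answer.
- 25/30 in both arms: p = 1.0, lower limit −19.3 points. There is no sign of a difference, yet non-inferiority is not shown.

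**The case against.** The strongest reply is that the chi-square test is not irrelevant to the design. A significant result in favour of the new technique shows superiority, which implies non-inferiority. A two-sided 5% test also spends 2.5% in that direction, so the two alpha levels need not conflict. Both points are correct. They cover about 42% of trials at the planning rates and leave the rest without a rule.

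Second, the SAP never says that p > 0.05 will be read as no difference. That is also correct. The 87% and 81% figures are rates of non-significance, and they become wrong conclusions only if someone reads them that way. The SAP offers no other reading.

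Third, a logistic regression of the primary endpoint is planned too, and an odds ratio can be turned into a risk difference given a reference rate. The SAP plans no such step.

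Fourth, the word difference in the endpoint may simply name the quantity compared, since non-inferiority also concerns a difference in rates. Taken alone, that wording would be a weak point. It matters here because no non-inferiority hypothesis is stated anywhere else.

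None of these replies supplies an analysis that uses the margin.

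**Conclusion.** The concern holds: the analysis is wrong as written and must be fixed. The stated 30 per group is a non-inferiority size, and no planned analysis tests non-inferiority. Under the plan's own rates, the specified test has about 41–42% power, against about 77–81% for the test the trial was sized for. About 36% of trials would meet the margin (Newcombe) without reaching p < 0.05.

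The figures assume 30 evaluable patients per arm, an absolute margin, one-sided alpha of 2.5%, and β = 80% read as power. The shortfall comes from the choice of analysis, not from the sample-size arithmetic. The roughly 80% also depends on a true 17.5-point advantage for the new technique. If the true rates were equal, the normal approximation gives only about 14% non-inferiority power at 72.5% remission, or 25% at 90%. That is a separate weakness, which this correction does not remove.

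**What to change.** In SAP 5.3, take the primary endpoint out of the general chi-square rule and specify:

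> The primary analysis estimates the difference in one-month remission rate (ligation and hemorrhoidopexy minus Doppler-guided ligation) with a two-sided 95% confidence interval by the Newcombe method. Non-inferiority is concluded if the lower limit is above −10 percentage points (one-sided alpha 2.5%). Superiority is claimed only if the lower limit is also above 0.

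Miettinen–Nurminen is a reasonable alternative, but one method must be named in advance. The superiority sentence is optional.

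Reword SAP 3.1 and protocol 3.6 to state this hypothesis. In SAP 5.1 and protocol 3.8, say that alpha is one-sided, that the margin is absolute, and that 80% is power. Because SAP 5.2 plans multiple imputation, also state how the interval is combined across imputed data sets, and name the analysis set to which the rule applies.

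**Cost.** Wording in two documents; no extra patients or data. Some results that might have been described as no difference become inconclusive. With the Newcombe interval, exact power at the planning rates is 77.5%, slightly under the nominal 80%.

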4.6 Covariates

The following data will be considered as covariates

- Demographics (Gender, Age, Weight, Height, ASA)
- Symptoms (Proptosis, Bleeding, Pruritus, Pain)
- Hemorrhoid Grade

5. Statistical Methodology

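### SAP 5.3 reports forward-selected covariate effects with ordinary 95% CIs, which selection invalidates, and does not name the SF-36 allocation contrast or adjust it for the pre-operative score

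*SAP*

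**What the plan says.** **Covariate models.** SAP 4.6 introduces its list with "The following data will be considered as covariates" and names five demographic variables (gender, age, weight, height, ASA), four symptoms (proptosis, bleeding, pruritus, pain) and hemorrhoid grade. SAP 5.3 states the scope as "Regression analysis will be applied to all distinct endpoints". For continuous outcomes "A Forward model will be introduced in our multiple linear regression analysis"; for binary outcomes "Similarly, a Forward model will be applied in our logistic regression analysis". The logistic terms get Wald tests, and "The odds ratios of each variable will be also estimated, alongside the respective 95%CI". The linear terms get a coefficient and a 95% CI. The SAP gives no entry level, no allowance for selection and no statement that these models are exploratory. The only threshold is general: "Statistical significance will be considered at the level of p value < 0.05".

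**Arm comparisons.** These are separate and unadjusted. "Continuous variables will be compared on the basis of an independent samples t-test", and categorical variables are compared by Pearson chi-square.

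**SF-36.** SAP 3.2 defines the endpoint as the difference at 1 month and 1 year relative to the pre-operative measurement, and lists three measurement times. SAP 5.3 plans a repeated measures ANOVA across the times and assesses allocation by an F-test. It does not say whether that is the group main effect or the group-by-time interaction. The pre-operative score is not among the SAP 4.6 covariates.

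**The concern.** A term kept because its p-value was small has, by that rule, an estimate far from no effect. An ordinary Wald test or 95% CI calculated afterwards ignores this. With about one event per candidate covariate, the trial could publish chance predictors of remission, recurrence or complications, with intervals that look like 95% CIs but are not.

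For SF-36, a repeated measures ANOVA with two arms gives at least two F-tests involving group. If neither is named, the choice can be made after the results are seen. The candidates also differ widely in power, and neither uses the pre-operative score as a covariate, although it is collected.

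**Working it through.** **1. Planning figures.** SAP 5.1 gives "the rate of the remission rate of symptoms, of patients who were submitted to hemorrhoidal artery ligation using ultrasound is 72.5" per cent for the Doppler arm and 90% for the other, with a 10-point margin. Reading alpha as one-sided 2.5% and the stated 80% as power:

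n = (1.960 + 0.842)² × (0.725×0.275 + 0.90×0.10) / (0.175 + 0.10)² = 30.03 per arm.

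This reproduces the stated 30.

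**2. Events per candidate.** Expected non-remissions = 30×0.275 + 30×0.10 = 8.25 + 3.00 = 11.25. Candidates = 5 + 4 + 1 = 10, so 1.1 events each. If 10% of patients are lost, about 10 events remain (11.25×0.9 = 10.1).

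**3. Chance selection.** Assume all 10 covariates are null and independent.
- Entry at 0.05: 1 − 0.95^10 = 40%.
- Entry at 0.01: 1 − 0.99^10 = 10%.
- Entry at 0.10: 1 − 0.90^10 = 65%.

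Forward logistic selection was simulated with 60 patients, the planning rates, 3 continuous and 7 binary null covariates, and score-test entry at 0.05. At least one term was selected in 40-42% of runs with independent covariates and binary prevalence 0.3-0.5. The range was 32-42% over prevalence 0.15-0.5 and correlation 0 or 0.3. Linear models gave 35-40%.

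**4. Coverage after selection.**
- Null terms, logistic: the Wald 95% CI covered an odds ratio of 1 in 25-33% of selections.
- Null terms, linear: coverage was 0-0.2%, because the entry test and the CI are essentially the same test.
- One binary covariate with a real effect:

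| True OR | Selected | CI covers truth when selected |
|---|---|---|
| 1.5 | about 10% | 66-78% |
| 2 | 16-17% | 76-93% |
| 3 | 33-36% | 93-98% |

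A continuous covariate with a true OR of 1.5 per SD was selected in 20% of runs, with a median reported OR of 2.5.

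**5. SF-36 power.** The documents give no effect size or correlation, so both are assumed. Take n = 30 per arm, SD 1, equal correlation r between times, and differences d1 (1 month) and d2 (1 year). Noncentralities:
- Main effect: ((d1+d2)/3)² / (2(1+2r)/(3n)), df 1, 58
- Group-by-time: (n/2) Σ(μ − mean μ)² / (1−r), with μ = (0, d1, d2), df 2, 116
- Baseline-adjusted average: ((d1+d2)/2)² / (2((1+r)/2 − r²)/n), df 1, 57
- Baseline-adjusted joint test: d′S⁻¹d, where S is 2/n times the matrix with 1−r² on the diagonal and r−r² off it, df 2, 56

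Example, d1 = d2 = 0.5 and r = 0.5: the noncentralities are 2.5, 5.0, 7.5 and 7.5, giving power 34%, 49%, 77% and 66%. The main effect averages in a time at which randomised arms cannot differ systematically, so it estimates (0 + 0.5 + 0.5)/3 = 0.33, a dilution of one third.

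Power (%) at r = 0.3/0.5/0.7:

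| Pattern (SD) | Main effect | Group-by-time | Adjusted average | Adjusted joint |
|---|---|---|---|---|
| 0.5, 0.5 | 41/34/30 | 37/49/72 | 72/77/89 | 61/66/81 |
| 0.5, 0.25 | 26/22/19 | 28/38/59 | 48/52/66 | 43/49/66 |
| 0.5, 0 | 14/12/11 | 37/49/72 | 25/27/36 | 43/53/74 |

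For the constant effect, the main effect's relative loss against the adjusted average is 1 − 0.412/0.720 = 43%, 1 − 0.343/0.768 = 55% and 1 − 0.295/0.887 = 67%. If the effect reverses sign (0.5, −0.5), group-by-time has 83.3/93.8/99.6% and the joint test 82.1/93.2/99.5%. The averaged test has no power beyond its 5% level there.

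**The case against.** **Little depends on the covariate models.** The SAP presents them as the effect of patient characteristics, and neither document ties a trial conclusion to them. This stands, and it limits the weight of the point. It does not rescue the intervals, which are planned for every endpoint with significance tests and no exploratory label.

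**Stronger readings of the selection problem.** A reader might infer that selection contaminates the primary comparison. It does not: the arms are compared separately by an unadjusted test. A reader might also count the absence of allocation from SAP 4.6 as a defect. The documents do not support that: no adjusted arm effect is promised, and the list does not say allocation is left out of the models. Nor are all selected intervals badly wrong; at a true OR of 3, coverage is close to nominal.

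**The 40% is a worst case and partly survives the fix.** It needs all 10 covariates null and an entry level that the SAP does not give. The 25-33% coverage depends on score-test entry followed by a Wald CI; entry by Wald test would bring it near zero. Showing 10 separate null estimates still leaves up to about 40% of endpoints with one interval excluding no effect (28% for remission in a simulation with one-covariate Wald CIs). This stands. The gain is complete display and intervals undistorted by selection, not fewer chance findings.

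**The SF-36 test may be sound.** Because the endpoint is change from pre-operative, group-by-time fits it best and has no dilution. That the pre-operative score is a level of the ANOVA is inferred from the three-time frame in SAP 3.2; SAP 5.3 does not list the levels. A reader might say that the planned test wastes most of its power. That would need the main-effect reading, and it fails even there at correlation 0.3 (41% against 72%). What remains is an unnamed contrast and an unused covariate.

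**Conclusion.** The covariate models are wrong as written: intervals reported after forward selection are not 95% CIs. The size is about 40% of models with a chance predictor and 25-33% coverage for selected null terms in logistic models (near zero in linear ones), if all covariates are null and entry is at 0.05. The shortfall is confined to null and weak covariates.

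The SF-36 part is a cheap improvement, not an error. Under a constant 0.5 SD effect, adjusting for the pre-operative score and averaging the follow-ups raises power over group-by-time from 37/49/72% to 72/77/89%. The main-effect reading would lose roughly 40% to two thirds of the attainable power. These figures rest on assumed effects and correlations. The advantage of averaging over group-by-time disappears if the benefit occurs at one follow-up only.

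**What to change.** **Covariate models (SAP 5.3).**
- Remove forward selection.
- Label patient-characteristic associations exploratory. Report the one-covariate estimate and 95% CI for all 10 covariates on each endpoint, stating that about one null interval in twenty will still exclude no effect.
- If an adjusted arm effect is to be reported, pre-specify the model with treatment forced in and very few baseline covariates.
- Leave the unadjusted arm comparisons outside this change. Whether the chi-square test answers the 10% margin question is a separate matter that this does not settle.

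**SF-36 (SAP 5.3).**
- Model the 1-month and 1-year scores with the pre-operative score as covariate.
- Name the tested contrast in advance: either the treatment effect averaged over both follow-ups, or a joint 2-df test of both. The joint test is the safer choice if the team has no view on whether the effect lasts.
- Report the difference and 95% CI at each time in either case.

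**Cost.** SAP wording only, on data already planned, and fewer predictor claims. The averaged test can lose up to about half the power of group-by-time when the benefit is at one follow-up only (36% against 72% at correlation 0.7). For a constant effect the joint test gives up about 8-13 points against the averaged test; the upper end is a case with unequal correlations (0.4, 0.3 and 0.6), 65.4% against 52.8%. Under sign reversal it gives up about 1 point or less against group-by-time.

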2.2 Research Group Experience

In a prospective 4-year study with a total of 90 patients²², the immediate post-operative and long-term course of patients undergoing DG-HAL hemorrhoid artery ligation was investigated. Totally, 64.4% of the included patients was discharged from the hospital, within 24 hours of the operation, 4.4% of patients needed additional analgesic treatment in the next 24 hours, while only 6.6% developed disease recurrence, one year after the operation. Additionally, a prospective randomized study of our clinic, compared pudendal nerve block and local anesthesia in 120 patients who underwent ultrasound scissors hemorrhoidectomy. A statistically significant lower rate of additional postoperative analgesic treatment was observed in the pudendal nerve block, while the level of postoperative pain, calculated on the Visual Analogue Scale (VAS scale), on the operative day was higher in the group of local anesthesia (5.1 vs. 2.2 $p < 0.001$)²³.

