3.9 Randomization

The randomization of the patients, between the two groups, will be performed using a software and a 1: 1 allocation ratio will be performed. Furthermore, an opaque envelope, which will contain the allocation group for the specific patient, will be opened preoperatively upon the entry of the patient into the surgical room, thus determining which technique will be applied.

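### SAP 5.3 judges covariates in logistic models by the Wald test with no sparse-data fallback; for rare endpoints in 60 patients this will often give unusable odds ratios and p near 1

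*SAP*

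**What the plan says.** SAP 5.3 sets out regression of the endpoints on patient characteristics, logistic for categorical outcomes, and its scope is complete: "Regression analysis will be applied to all distinct endpoints". Variables are chosen by a forward procedure whose entry statistic is not given. For the logistic models, "The statistical significance of each variable will be calculated by the Wald test", and an odds ratio with a 95% CI is reported for each variable. The assumption checks listed for these models cover independence, exclusive and exhaustive categories, and linearity in the logit. None concerns empty cells or separation. No minimum number of events is set, and no exact, likelihood-ratio or penalised alternative is named.

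The covariates in SAP 4.6 are demographics (gender, age, weight, height, ASA), hemorrhoid grade and "Symptoms (Proptosis, Bleeding, Pruritus, Pain"). Six of these are naturally binary: gender, ASA (only I and II are eligible) and the four symptoms. Allocation is not on the list. The comparison of categorical data between groups is a Pearson chi-square test.

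On size, SAP 5.1 says "Totally, the required number of patients is 60". The only rate the documents give for a secondary yes/no endpoint is in Protocol 2.2, from the group's earlier Doppler-guided series: "only 6.6% developed disease recurrence, one year after the operation".

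**The concern.** When every event falls in one level of a binary covariate, the maximum-likelihood log odds ratio has no finite value. The software stops at a large estimate with a far larger standard error. Their ratio is close to zero, so the Wald p is close to 1. The rule therefore fails in an awkward direction: a predictor with one event in its low-risk level can be significant, and the same predictor with none cannot.

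What is at stake is the set of covariate models for the rarer endpoints. A strong predictor could be reported as irrelevant, beside an odds ratio and interval that mean nothing. This is a different fault from the bias of forward selection. Forcing every covariate into the model, or calling the models exploratory, would leave it in place.

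**Working it through.** **Inputs.** Total 60, from SAP 5.1. Allocation: "a 1: 1 allocation ratio will be performed" (Protocol 3.9), so 30 per arm. Recurrence 6.6% (Protocol 2.2). Planned remission from SAP 5.1: "hemorrhoidal artery ligation using ultrasound is 72.5" per cent in the control arm, and "the respective rate of the ligation and hemorrhoidopexy technique is 90" per cent. Covariate prevalences and all other secondary event rates are not given, so ranges are assumed.

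**The plan's own figure.** With an unpooled variance and one-sided α of 2.5%, n = (0.725×0.275 + 0.90×0.10) × (1.960 + 0.842)² / (0.90 − 0.725 + 0.10)² = 30.03 per group. This matches the stated 30, or 31 if rounded up.

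**Number of yes/no endpoints.** Primary 1, in hospital 6, at 7 days 4, at 1 year 6 (including reoperation), recurrence 1: total 18.

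**What an empty cell does.** Newton-Raphson fits (20 iterations), 30 patients per level:

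| Events | log OR | SE | Wald p | Likelihood-ratio p | Fisher p |
|---|---|---|---|---|---|
| 5 v 0 | 19.59 | 7338 | 0.998 | 0.007 | 0.052 |
| 8 v 0 | 20.19 | 7338 | 0.998 | 0.0004 | 0.005 |
| 30 v 0 | 42.41 | 10378 | 0.997 | <0.00001 | <0.00001 |
| 8 v 1 | 2.36 | 1.1 | 0.032 | 0.007 | 0.026 |

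Stopping at 10 iterations gives Wald p = 0.84 for 8 v 0, still far from significant.

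**How often one level is empty.** For event rate r in both levels, of sizes m and 60 − m, the chance that exactly one level has no events is q₁(1 − q₂) + q₂(1 − q₁), with q₁ = (1 − r)^m and q₂ = (1 − r)^(60−m).

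| r | m = 30 | m = 12 |
|---|---|---|
| 2% | 50% | 57% |
| 5% | 34% | 53% |
| 6.6% | 22% | 45% |
| 10% | 8% | 28.5% |
| 20% | 0.2% | 7% |

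**Six covariates, four events.** 0.066 × 60 = 3.96, about 4 events. For a covariate unrelated to outcome and held by m of 60, P = [C(m,4) + C(60−m,4)] / C(60,4), with C(60,4) = 487,635. For six independent covariates the chance of at least one empty cell is 1 − (1 − P)⁶.

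- m = 30: P = 2×27,405/487,635 = 0.112, giving 51%.
- m = 18: P = (3,060 + 111,930)/487,635 = 0.236, giving 80%.
- m = 12: P = (495 + 194,580)/487,635 = 0.400, giving 95%.

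These are the chances that at least one covariate has an unusable odds ratio when fitted. Whether it is fitted depends on the unstated entry rule.

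**Power in an assumed example.** True rates 20% v 1%, 30 per level, all tables enumerated: an empty cell occurs in 74%. The Wald rule rejects in 9%, Fisher's exact test in 48% and the likelihood-ratio test in 84%.

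**Primary endpoint.** The rarer outcome is non-remission: 30×0.275 + 30×0.10 = 11.25 expected. The chance that the 90% arm has none is 0.90³⁰ = 4%. With 11 non-remitters, the chance that a given covariate has an empty cell is 0.03%, 1.2% or 6.6% at prevalence 50%, 30% or 20%. These are the 10-event values (0.08%, 1.95%, 8.7%) multiplied by 20/50, 32/50 and 38/50.

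**The case against.** The strongest objection concerns what the 51%, 80% and 95% mean. A reader might infer that they are the chance of missing a real effect. They are not, because they scatter the events at random and so assume no covariate effect. At 20% prevalence almost all of the 0.400 comes from the four events falling in the larger level (0.399). That table, 0/12 v 4/48, has Fisher p = 0.57 and likelihood-ratio p = 0.17, so a non-significant verdict is right. The striking pattern, all four in the smaller level, has a chance of 0.001 per covariate and 0.6% across six; at 30% prevalence it is 3.7% across six. This objection stands. The figures count unusable odds ratios only.

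A reader might also set the Wald rule's 9% against the likelihood-ratio test's 84%. That overstates the loss. The likelihood-ratio test is liberal in sparse tables: at 30 per level its type I error is 8.3% at a 5% event rate and 8.9% at 6.6%. Fisher's 48% is the safer benchmark, though that test is conservative. The 20% v 1% scenario is assumed and has no source in the documents.

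A third tempting reading is that treatment comparisons are compromised. The documents do not support it. The regression concerns patient characteristics, SAP 4.6 does not list allocation, and the comparisons between arms use chi-square, which does not fail in this way (0 v 6: p = 0.010).

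Finally, most event rates are unknown, and at 15–20% an even split is rarely empty. That limits the point to the rarer endpoints. It does not supply the missing rule. A minimum count would remove most of the problem, but at 10 events and 20% prevalence the chance of at least one empty cell among six covariates is still 1 − (1 − 0.087)⁶ = 42%.

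**Conclusion.** The point holds for the secondary covariate models of the rarer yes/no endpoints. At rates of about 5–7% or below, empty covariate levels will be frequent with 60 patients. In each such case the stated rule returns p near 1 and an unusable odds ratio and interval, whatever the strength of the association. The unstated entry statistic does not rescue it. Under score or likelihood-ratio entry, a separated variable can enter and then be reported with p near 1; under Wald entry it would not enter at all.

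The failure of the Wald test with an empty cell needs no assumption. Its frequency rests on three: event rates (only the 6.6% is documented, from a Doppler-guided series), covariate prevalences of 20–50%, and independence between covariates. The loss of power for a real effect is illustrated by one assumed scenario, 9% against 48% for Fisher.

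The arm comparisons are untouched. The primary endpoint is largely spared at its planned rates, although uncommon covariates could still produce an empty cell there. This is worth correcting before analysis, but it does not put the trial's main conclusion at risk.

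**What to change.** In SAP 5.3:

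- Fit a logistic model only when the rarer outcome of the endpoint reaches a pre-stated count, for example 10. Count the rarer outcome rather than events: for the primary endpoint that is non-remission.
- Below that count, report numbers by covariate level and arm, with Fisher's exact test if a test is wanted.
- Where a model is fitted, replace the Wald test and interval with Firth penalised logistic regression, using profile-likelihood tests and 95% CIs, at least whenever a cell is empty.

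The cost is SAP wording and a routine outside the standard SPSS procedures. Recruitment, treatment and data collection do not change. The rarest endpoints would have no covariate model; at about 4 expected events that would include recurrence, where such a model could say little. Fixing the rule now also avoids choosing a rescue method after separation has appeared in the data.
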